## Secondary Outcome Variables

Secondary Measures. (1) Monthly percentage of on-time (i.e., within three hours of the scheduled time set by patient-physician agreement) bottle openings as measured by MEMS and self-report, respectively. Note that this is different from the primary measure which dichotomizes adherence (Y/N) with a 95% threshold. The primary measure is the measure of greatest clinical significance. The secondary measure is more sensitive to changes in behavior; (2) CD4 counts and HIV-1 RNA levels obtained at primary care visits.

Exploratory Measures. (1) MOS-HIV physical health and mental health summary scores (0-100) across the study period; (2) self-reported days of opiate and cocaine use.

Usage, Acceptability, and Cost Measures. Outcomes related to the usage and acceptability of the Smartphone application will include Acceptability Questionnaire total score, SUMI global scale score, average uses per day, and average duration of use per day. Outcomes related to the cost of the intervention will include total cost of the intervention per person, and the incremental cost-effectiveness ratio (ICER). To calculate ICER, we will divide the costs of the intervention by the difference between the two groups in terms of the percent of participants who take 95% of prescribed doses of their antiretroviral medication. The ICER can be interpreted as dollars spent per unit of desired outcomes gained. In addition, a more complete cost/benefit analysis conducted by academic economists will be included in a future large-scale study.

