If they express interest in learning more, the doctor will contact the staff member at the doctor's office who is in charge of study recruitment and assessment (hereafter, outreach coordinator). The person who is currently serving in this role is [name]. [name] has a bachelor's of science in nursing and a masters of education. She regularly consults with Comprehensive Care Practice patients regarding the importance of medication adherence and helps them address barriers to adherence and access to care. [name] is a JHU employee who is listed on the JHU IRB protocol as a study team member, has completed all training required by the JHU IRB, and is approved by the JHU IRB as a consent designee for this study. The outreach coordinator will go upstairs to CCP and wait for the patient to finish their appointment. Once the appointment is complete, the outreach coordinator will escort the patient to their office. The outreach coordinator will briefly explain the intake interview process and basic purpose of the study.

**Script for outreach coordinator:** *As you know, I am recruiting participants for a research study. This study is about a smartphone-based intervention for medication adherence that makes it easier for users to contact their care providers, provides users with reminders to take their medicine, and pays users money when they submit videos of themselves taking their pills each day. Half of the people who join this study will be randomly selected to receive the smartphone-based intervention, which we call SteadyRx. All of the people who join this study will get paid \$30 per month for participating in interviews and \$20 for bringing me a special electronic pill bottle that we will use to hold your medicine that tracks when you open the bottle, a total of \$50 per month. If you are interested in joining this study, then I will help you to do that. We will need to schedule another appointment in order to move forward. During this appointment, we will go through a study consent form together that explains the study in detail. Then I will ask you questions that will allow me to assess whether you qualify to take part in this study. The whole process will take about two hours. Since it includes an interview, you will be paid \$50 if you complete this process, whether or not it turns out you qualify for the study. Would you like to proceed?*

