The [Addiction Severity Index-Lite](#) which assesses drug use and related problem severity

The [Patient Reactions Assessment](#) is a 15-item validated instrument for assessing a patient's perceived ability to initiate communication about their illness. This will allow us to determine whether the consult element of SteadyRx has an effect on patient's perceptions of the quality of their communication with their provider.

After the intake interview is completed, the staff member should review and complete [the Inclusion/Exclusion checklist](#). If the participant is eligible, then he/she should be informed that he/she is a candidate for diversion to treatment and he/she is invited to participate in a research study.

Any participant who is ineligible should be informed that they are not eligible to participate in the study. Upon notification of ineligibility, some participants may be saddened or angered. See the section on study eligibility for further details describing how to handle ineligible participants. Be sure to retain all completed assessments, independent of whether a participant was eligible for the study. Assessments completed by ineligible participants will be collected and stored separately from assessments completed by eligible participants.

**CD4 counts and HIV-1 RNA levels.** The participants will sign a separate consent form granting their care provider (i.e., Comprehensive Care Practice) permission to share their test results with the study team. Thus, we anticipate that we will have a baseline measure and two study period measures of [CD4 and HIV-1 RNA levels](#) for pilot study participants. We will also maintain a record of scheduled appointments and whether the participant attended each appointment (Y/N; coded yes for any appointment attended within one week of the originally scheduled date). Importantly, we will be collecting our monthly assessments on the same day as the patient is scheduled to have their CD4 and HIV-1 RNA levels checked in the same building. Note that we do not plan to interface directly with

the existing medical records systems used by care providers. Instead, care providers will submit the information to the outreach coordinator, who will relay the information to the study team in Kalamazoo via the phone.

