### Procedures

**Overview.** All staff will be prepared for the intake assessment. After the informed consent is signed by the participant, the Outreach Coordinator notifies the WMU staff and brings the participant to the computer terminal. Student investigators will have the primary responsibility for randomly assigning participants to one of the two study conditions. After completing the randomization procedure, the Outreach Coordinator and WMU staff should train participants how to use the SteadyRx app and PillWatch function (if in SteadyRx group), distribute CTPayer card, and update relevant data logs.

**Randomization Variables.** The proposed pilot study will feature a 2 group, randomized controlled, parallel group design. In order to assess the effectiveness of the proposed intervention as a whole, participants will be assigned to receive usual care (Control Group) or the SteadyRx smartphone intervention. A computerized urn randomization procedure will be used to randomize participants and balance groups on three baseline characteristics that may independently influence the main outcome measures of ART adherence and viral load. Specifically, depression, active drug use, and low health literacy have all been shown to be associated with reductions in ART adherence. Thus, we will use presence of current depression (Y/N); self-reported recent Cocaine or Opiate use (Y/N); and TOFHLA (a health literacy measure; see Assessments) score  $\leq$  the rolling median (Y/N) as the stratification variables in the present study. While it might be desirable to stratify on additional variables, increasing the number of variables is not practical given the study's sample size.

**Procedure.** After obtaining informed consent, the student investigator will complete the intake interview. First, the ASI-Lite will be administered to finish determining eligibility. If the participant is eligible for the study, the TOFHLA will be administered. While the participant is completing the ASI-Lite and the TOFHLA, the student investigator will call the Outreach Coordinator to obtain depression status, CD4 count, HIV-1 RNA levels, and drugs of abuse history information. Once the participant has completed the TOFHLA and information regarding recent drug use and depression status, group assignment can be determined. The student investigator will then call the principal investigator,

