### **Analytic plan for SteadyRx study**

Descriptive statistics (means and standard deviations or proportions) will be calculated for demographics, baseline participant factors (e.g., quality of life, substance use), treatment history, health literacy, and application ratings and engagement. All analyses will be intent to treat; all participants who are randomized will be included. All analyses will be adjusted for the pre-specified covariates used for stratification. All hypothesis tests will be two-sided,  $\alpha$  will be set at 0.05, and p-values for secondary analyses will be corrected to maintain  $\alpha=0.05$ . Based on our past research and the automated collection of our primary outcome measure, we expect relatively little missing data and little difference in the rates of missing data across groups. We plan to conduct analyses in which missing samples are assumed to represent the adverse outcome (e.g., missing = drug positive) and in which missing data will be ignored (missing = missing). The “missing positive” method is more conservative and will be considered the primary method.

Primary Outcomes. The effects of the intervention relative to the control group on the dichotomous monthly adherence measure will be analyzed with a longitudinal logistic regression model with treatment group and time as covariates. The group term, representing the between-group difference averaged over time, will be the primary coefficient of interest. Correlation among outcomes over time within individuals will be handled using the method of Generalized Estimating Equations (GEE). The dichotomous viral load variable (<400 HIV-RNA/mL, y/n) will be modeled with an analogous model but with only two follow-up measures.

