Secondary and Exploratory Analyses. Continuous measures assessed repeatedly over time (bottle openings, CD4, HIV-1 RNA, and MOS-HIV) will be analyzed using a longitudinal linear regression model, analogous to that used for the primary outcomes. We will control for baseline values in the CD4, viral load, and MOS-HIV models. Measures assessed only at intake will be analyzed via linear or logistic regression as appropriate. Baseline predictors of response to treatment, including positive urine screen for cocaine or opioids, health literacy (TOFHLA), depression (BDI), psychological factors (SCL-90), job and educational history (VEA), and executive function (Wisconsin Card Sorting) will be assessed by fitting regression models with interactions between treatment assignment and each predictor variable, to determine if the effect of treatment on outcome varies as a function of each of these predictors. Similar models, with an interaction between treatment group and drug use, adherence to buprenorphine/methadone, and attendance to primary care, respectively, (as time-varying covariates) will allow us to determine whether these variables affects response to treatment.

Usage, Acceptability, and Cost. Acceptability and SUMI global scale scores, app uses per day, daily duration of use, and cost of the app and incentives and ICER will be summarized via descriptive statistics (mean, SD, medians, histograms).

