### **Data Analysis to be reported in future publication**

Groups were compared on intake variables using Fisher’s exact tests for dichotomous variables, chi-square tests for categorical variables with more than two categories, and t-tests for continuous variables. Outcome measures were analyzed using generalized estimating equations (GEE) (Zeger, Liang, & Albert, 1988), including and excluding the stratification variables as covariates. GEE results presented use the covariate model unless otherwise specified. Planned comparison t-tests were used to compare between and within groups on outcome measures at time points 1 and 6. Analyses were intent-to-treat and conducted using SAS version 9.3. Missing data were treated as missing-missing. Analyses were two-tailed with statistical significance set at alpha of .05. Due to the error in the collection of biometric data, analyses for these variables are not included.

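### Group interactions with drug use, opioid-treatment adherence and clinic attendance measured after randomisation can show only descriptive associations, not what affects response to SteadyRx

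*Combined protocol and SAP*

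**What the plan says.** The analytic plan first describes baseline predictors of response, each tested by its interaction with treatment. It then carries the same model over to three variables observed during follow-up: drug use, adherence to buprenorphine/methadone, and attendance at primary care. These enter "as time-varying covariates) will allow us to determine whether these variables affects response to treatment".

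Other parts of the document bear on this:

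- On-study drug use is itself an exploratory measure (Secondary Outcome Variables): "self-reported days of opiate and cocaine use".
- Under Randomization Variables, "depression, active drug use, and low health literacy have all been shown to be associated with reductions in ART adherence". The urn balances groups on baseline characteristics only; for drug use, this is recent use reported at intake.
- The recruitment script under Identifying Participants says the intervention "makes it easier for users to contact their care providers".
- Attendance is logged on study (CD4 counts and HIV-1 RNA levels paragraph): "We will also maintain a record of scheduled appointments and whether the participant attended each appointment".
- The only adjustment named is general: "All analyses will be adjusted for the pre-specified covariates used for stratification".

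The analytic plan gives no lag between covariate and outcome, no method for covariates that treatment may change, and no caveat on interpretation. The section on data analysis for future publication supplies none either.

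**The concern.** A baseline moderator is fixed before assignment, so within each of its levels the two arms remain comparable. A variable measured in month 3 has no such protection. If SteadyRx alters who uses drugs or who attends, SteadyRx and control participants at the same level of that variable are different kinds of people. If they also differ on something that drives adherence, the group contrast within the level is distorted, and the interaction may be too.

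Even without that distortion, the interaction says that the group difference varies with a concurrent behaviour. It does not say that the behaviour changes the response. The planned sentence promises the second. At stake is whether a pilot hands a future larger study an unsupported account of what modifies the effect, whether positive or null.

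**Working it through.** The plan gives no effect size, event rate or power for these models, so there is no figure of its own to reproduce. N = 50 (taken as 25 per arm) and six monthly assessments come from the document. All other inputs are assumptions.

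**1. Bias in the interaction, large sample, no true treatment effect.** Let u be an unmeasured standard normal trait. Set logit P(adherent) = a + s·u and logit P(variable present) = b + t·u. Adherence is 50%, control prevalence is 40% or 62%, and s = t = 1, 1.5 or 2 in the control arm. Within each arm, integrate over u to get the odds ratio (OR) between variable and adherence. The interaction OR is the SteadyRx value divided by the control value; its true value is 1.

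| What treatment does to the variable | False interaction OR, unadjusted |
|---|---|
| Nothing, or no shared cause | 1.00 |
| Shifts prevalence only, by up to 28 points | about 1.0 to 1.38 |
| Halves the link t, equal prevalence | 0.54 to 0.73 |
| Removes the link t, equal prevalence | 0.18 to 0.49 |

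The last row can be checked by hand. With no link, the SteadyRx OR is 1, so the interaction OR is the reciprocal of the control OR. At 62% prevalence and slope 2 the control OR is 5.42, and 1/5.42 = 0.18.

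In the shift-only case, adjusting for the three stratifiers lowers the upper end to 1.31 if they explain 25 to 50% of the trait. The treatment ORs within levels of the variable, which the plan does not say it will report, run from 0.46 to 0.93 unadjusted although the true value is 1.

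**2. How often N = 50 would show this.** The model was an independence GEE with six monthly records, cluster-robust standard errors and stratifiers adjusted, tested at a nominal 5%.

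- Shift-only: 3.4 to 7.2% rejection with a prevalence gap, against 5.2 to 7.5% without one.
- Link halved: 6.5 to 16%. Link removed: 13 to 67%. With the link unchanged, the same set of runs gave 5 to 6%.

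A separate simulation used a continuous outcome with a true group effect of 0.5 for everyone. It showed the same pattern. Shift-only left the interaction near zero (−0.02 and −0.07) but pulled the within-level group effects down to 0.30–0.32 and 0.11–0.19. Halving or removing the link gave false interactions of 0.40 and 1.06, with 15% and 81% rejection.

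**3. Precision with the binary 95% adherence outcome.** With no prevalence gap, the SD of the log interaction OR is 0.535 to 0.726. The 95% interval therefore spans exp(1.96 × 0.535) = 2.9 to exp(1.96 × 0.726) = 4.1 either way. Power is 15 to 24% for a real interaction OR of 2, and 28 to 48% for 3.

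**4. Precision with a continuous outcome**, in SD units, with 50% prevalence and within-person correlation ρ of 0.3 to 0.7.

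- Covariate stable within person: SE = √[(1+5ρ)/6] × √[2(1/12.5 + 1/12.5)] = 0.365 to 0.490. The half-width is 1.96 × SE = 0.72 to 0.96.
- Covariate varying freely from month to month: SE = √[2(1−ρ)/(25 × 5 × 0.25)] = 0.212 at ρ = 0.3 and 0.139 at ρ = 0.7. The half-width is 0.41 down to 0.27.

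**The case against.** The strongest reply is that these analyses sit under a heading that includes the word exploratory, in a self-described pilot. The preceding sentence speaks only of the treatment effect varying with a predictor, so the wording at issue may be loose language for a statistical interaction. The section on data analysis for publication says "Outcome measures were analyzed using generalized estimating equations (GEE" and lists no such interactions. This supports a minor grading. It does not remove the point: that section does not withdraw the interactions, and the sentence as written promises a determination.

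The low precision is not special to this sentence. It applies equally to the planned baseline interactions and is expected in a pilot. That stands; only the post-randomisation issue is distinctive.

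A reader might go further in four directions that the documents do not support:

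- **That SteadyRx does change these variables, so the results will be biased.** Nothing in the document shows this. It shows only that such an effect is possible.
- **That equal prevalence in the two arms makes the interaction safe.** This holds only if treatment shifts prevalence and nothing else. The link-weakening rows above show bias with no gap at all.
- **That N = 50 is too small for these interactions to show anything.** The wide intervals above are for the binary outcome or a covariate stable within person. Imprecision may be milder for the percentage of on-time openings, or for a covariate that moves freely within person.
- **That the primary result is compromised.** The primary models contain none of these covariates.

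**Conclusion.** The concern holds as a minor point about the stated inference. Because the three covariates are measured after randomisation and may be affected by treatment, the planned interactions describe an association and cannot settle whether those behaviours modify the effect of SteadyRx.

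The amount of bias is not knowable from the document. It ranges from none to a false interaction OR of about 1.4 in one direction or about 0.2 in the other, according to whether treatment leaves the variable alone, shifts its frequency, or weakens its link with an unmeasured cause of adherence. These figures rest on assumed prevalence, slopes and adherence rate, with no adjustment. Covariate adjustment helps only so far as the stratifiers capture the shared cause. An interval spanning a factor of about 3 to 4 either way for the binary outcome is likely, on the same kind of assumptions.

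**What to change.** 1. Replace the claim that the time-varying interactions will determine what affects response. State instead that they will be reported as descriptive associations with 95% confidence intervals, and not as evidence that these variables modify the treatment effect.
2. Compare on-study drug use (already an exploratory measure) and primary care attendance between groups as outcomes, and report the result beside any time-varying interaction.
3. Rest statements about effect modification on the baseline interactions already planned, using intake variables that the document lists as collected: ASI-Lite cocaine/opiate use, TOFHLA and BDI-II. Label them exploratory and give 95% confidence intervals.
4. Keep the buprenorphine/methadone interaction only if an on-study measure exists. Neither the intake interview list nor the monthly assessment list names a dedicated one.

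The cost is a change of wording in the analysis plan and one extra group comparison from data already recorded. The downside is that the time-varying question is answered descriptively only. The baseline interactions will also remain imprecise at this sample size, so the intervals should accompany them.

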### Design

This randomized controlled pilot study features a parallel group design. Participants (N = 50) will be randomly assigned to one of the two groups: Treatment as usual (TAU) or the SteadyRx-supported antiretroviral adherence group (SteadyRx). We will randomize using urn stratification to promote equal numbers of individuals in each group and balanced distributions within a dichotomized covariate expected to be associated with the outcome. Stratification variables are current depression (Y/N); self-report of problem drug use in the last 30 days (Y/N); and TOFHLA score  $\leq$  the rolling median (Y/N). Study participation will last for six months from the date of randomization.

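### The ICER is a single group-level ratio, so the planned mean, SD, median and histogram do not apply to it, and its numerator, unit and time window are not stated

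*Combined protocol and SAP*

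**What the plan says.** The cost outcomes are introduced under Secondary Outcome Variables: "Outcomes related to the cost of the intervention will include total cost of the intervention per person, and the incremental cost-effectiveness ratio (ICER"). The ICER is then defined: "we will divide the costs of the intervention by the difference between the two groups in terms of the percent of participants" who reach the 95% dosing threshold. Its reading is given as follows: "The ICER can be interpreted as dollars spent per unit of desired outcomes gained". The same paragraph limits the scope: "a more complete cost/benefit analysis conducted by academic economists will be included in a future large-scale study".

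In the Analytic plan for SteadyRx study, the closing paragraph places the ICER in one list with acceptability and SUMI scores, app use, and app and incentive cost. It applies one set of summaries to the whole list: "cost of the app and incentives and ICER will be summarized via descriptive statistics (mean, SD, medians, histograms"). Neither section gives an interval, a resampling step or any other uncertainty method for the ICER.

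**The concern.** Every other item in that list has a value for each SteadyRx participant. The ICER does not, because its denominator exists only after the two arms have been compared. An analyst following the sentence literally would have to invent participant-level ICERs. The only obvious way is to divide each person's cost by the one observed difference. The resulting SD and histogram would look like uncertainty in cost-effectiveness but would show only variation in cost.

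The definition also leaves three choices open: whether the numerator is per person and net of any payment made in both arms; whether the unit is a percentage point or one additional adherent participant; and which of the six monthly adherence measures supplies the difference. At stake is a named outcome of the pilot that could be reported with a misleading spread, or computed differently by two analysts.

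**Working it through.** **No figure to reproduce.** The documents state no ICER, no total cost and no precision for either. What follows is reasoning from the definition, plus illustrations whose assumptions are labelled.

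**1. Number of ICERs.** Write C for cost and D for the difference in the proportion adherent. D is one number per trial, so ICER = C / D is one number per trial. An SD or histogram of it needs a resampling distribution, and none is planned.

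**2. What the literal rule would produce.** Assume a per-person cost with mean $800 and SD $300, 25 per arm (from "Participants (N = 50) will be randomly assigned to one of the two groups", with equal arms assumed), and single-month adherence of 20% (control) and 40% (SteadyRx).
- ICER = 800 / 0.20 = $4,000 per additional adherent participant.
- SD of cost divided by the fixed D = 300 / 0.20 = $1,500. This contains nothing about the error in D.
- SE of D = √[(0.20×0.80 + 0.40×0.60) / 25] = √0.016 = 0.1265.
- Approximate squared relative error from mean cost: (300/√25 / 800)² = 0.075² = 0.0056.
- Squared relative error from D: (0.1265 / 0.20)² = 0.40.
- Share due to D: 0.40 / 0.4056 = 99%.

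Under these inputs, the literal summary leaves out nearly all of the ICER's sampling error. The first-order approximation is rough for so noisy a ratio, but the ordering is clear.

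**3. How often D is at or below zero (single month, 25 per arm, exact binomial).**

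| Control v SteadyRx (assumed) | D = 0 | D ≤ 0 |
|---|---|---|
| 20% v 40% | 3.6% | 7.8% |
| 20% v 60% | 0.1% | 0.2% |
| 30% v 40% | 9.0% | 27.5% |
| 30% v 50% | 4.0% | 9.3% |
| 30% v 60% | 1.0% | 2.0% |

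At 20% v 40%, the simulated 95% range of the ICER among draws with D above zero is about $1,700 to $20,400.

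**4. Six-month average.** With a constant within-person correlation ρ, the variance of D is multiplied by (1 + 5ρ)/6. Again at 20% v 40%:

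| ρ (assumed) | SE of D | 95% interval, points |
|---|---|---|
| single month | 0.1265 | −5 to +45 |
| 0.3 | 0.0816 | +4 to +36 |
| 0.5 | 0.0966 | +1 to +39 |
| 0.7 | 0.1095 | −1 to +41 |

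**5. The numerator and payments in both arms.** Maximum incentives per SteadyRx participant over 180 days, counting three-day bonuses without overlap:
- daily credits: 180 × $2 = $360
- three-day bonuses: 60 × $6 = $360
- 30-day bonuses: 6 × $20 = $120
- undetectable viral load: 2 × $100 = $200
- returned phone: $100
- total: $1,140

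The viral-load payment appears in Monthly Assessments, within the General Procedures that cover all randomised participants. It appears again in the SteadyRx procedures (Assessing Videos in SteadyRx). If both arms receive it, up to $200 of $1,140 (17.5%) is not incremental, leaving $940. At an assumed 30-point difference, the ICER is then $31 per point instead of $38 (1,140/30). App, phone service and staff costs are not in the documents, so these amounts cover incentives only.

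**6. Unit.** $38 per percentage point and $3,800 per additional adherent participant are the same result. The label decides which is printed.

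**The case against.** The strongest reply is that the ICER was swept into a loosely worded list, and that a sensible analyst would report one number. The definition supplies a formula and an interpretation. Per-person cost is named immediately before the ICER, so a per-person numerator is the natural reading. Control participants receive no app, study phone or video incentives, so the intervention's cost is already largely incremental. The primary model's group term is a time-averaged contrast, which is an obvious default for the denominator. The ICER is neither a primary nor a secondary measure, no test depends on it, and a fuller economic analysis is deferred to a later study.

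Most of this stands and sets the severity. It does not remove the point: the stated rule is wrong for this quantity, and the pilot still names the ICER as an outcome.

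A reader might infer more than the documents support:
- **That the cost-effectiveness analysis cannot be produced or interpreted.** A point ICER can be calculated unless D is exactly zero, and app and incentive costs can properly be summarised by mean, SD, median and histogram.
- **That the numerator is not an incremental per-person cost.** The text leaves it unspecified and does not rule that reading out.
- **That the ICER is uncertain 25-fold.** This requires dividing a whole arm's cost by a difference in proportions. The plan does not propose it, and the neighbouring per-person wording points away from it.
- **That the adherence difference has an interval spanning zero.** This depends on the assumed rates and on using a single month. With the six-month average it reverses at correlations of 0.3 and 0.5.

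**Conclusion.** The point holds as a minor one. The planned descriptive summary does not fit a ratio with a group-level denominator, and a literal application would give a spread that omits the error in the adherence difference. That conclusion follows from the two sections alone. The missing numerator, unit and time window are gaps with natural default readings. The documented effect on incremental cost is at most $200 per person, and only if the viral-load payment is made in both arms.

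The sizes rest on assumptions: equal arms of 25, the adherence rates shown, constant within-person correlation, and an $800 mean and $300 SD for cost. They show why an uncertainty method is useful; they do not predict how unstable this trial's ICER will be.

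**What to change.** In the Usage, Acceptability, and Cost paragraph of the analytic plan, limit mean, SD, median and histogram to participant-level measures, including per-person cost. Then define one ICER:

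ICER = (mean cost per SteadyRx participant − mean cost per control participant) / (difference in the proportion reaching 95% adherence, averaged over the six months).

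State the unit. Give its uncertainty by a bootstrap that resamples participants within arm and carries cost and adherence together. If the difference may be near zero, show the draws on a cost-effectiveness plane, because a percentile interval for the ratio is then hard to read.

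Reconcile the Monthly Assessments text with the SteadyRx procedures on which arm receives the viral-load payment, so that the cost difference is computed from what was actually paid.

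The change costs a few lines of plan text and a short program, using cost and adherence data that the trial already collects. The reported ICER will look less precise. This does not require the fuller economic analysis deferred to a later study.
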